2.4 Sample size calculation

AFI of the fingertip is a completely new application, there are no data on the basis of which a sample-size calculation can be done. It is a pilot study. The results of this pilot will serve to calculate a sample size for a follow-up study.

3. TREATMENT OF SUBJECTS

3.1 Investigational product/treatment

3.2 the intervention with lidocaine / prilocaine cream and with capsaicin 8% patches is not the aim of the study, but serves as a negative control.

3.3 Use of co-intervention (if applicable)

n.a.

3.4 Escape medication (if applicable)

n.a.

4. INVESTIGATIONAL PRODUCT

4.1 Name and description of investigational product(s)

4.2 Summary of findings from non-clinical studies

n.a.

4.3 Summary of findings from clinical studies

n.a.

4.4 Summary of known and potential risks and benefits

n.a.

4.5 Description and justification of route of administration and dosage

n.a.

4.6 Dosages, dosage modifications and method of administration

n.a.

4.7 Preparation and labelling of Investigational Medicinal Product

n.a.

4.8 Drug accountability

n.a.

5. NON-INVESTIGATIONAL PRODUCT

5.1 Name and description of non-investigational product(s)

- lidocaine/prilocaine creme (EMLA)
- capsaicine 8% patch (Qutenza)

5.2 Summary of findings from non-clinical studies

- EMLA: zie de SPC, <http://db.cbg-meb.nl/IB-teksten/h11015.pdf>
- Qutenza: zie de SPC, <http://www.astellas.nl/sites/default/files/SmPC%20Qutenza.pdf>

5.3 Summary of findings from clinical studies

- EMLA: zie de SPC, <http://db.cbg-meb.nl/IB-teksten/h11015.pdf>
- Qutenza: zie de SPC, <http://www.astellas.nl/sites/default/files/SmPC%20Qutenza.pdf>

5.4 Summary of known and potential risks and benefits

-EMLA 5% (from SmPC) Common (>1/100): Transient local reactions at the application site such as paleness, erythema (redness) and oedema. An initial and usually mild sensation of burning, itching or warmth at the application site. Uncommon (1/1000 to 1/100): An initial mild burning, itching sensation or warmth at the application site; local paresthesia at the application site, e.g. tingling sensation; and skin irritation at the application site. Rare (<1/1000): Methaemoglobinaemia (especially at longer application time in children with atopic dermatitis or mollusca contagiosa). Corneal irritation after accidental eye exposure.

-Qutenza 8% patch: On application a sensation of prickling and/or burning will occur for approximately 180 minutes, together with an area of erythema of the skin. In case of severe pain, a cold pack can be applied to the site of application to reduce pain, and oral analgesics, such as paracetamol, can also be provided. Hypersensitivity to pressure and heat can occur for up to two days. As with any medication, rare side effects cannot be excluded beforehand.

5.5 Description and justification of route of administration and dosage

- the route and dosage of lidocaine/prilocaine and the capsaicin patch is being used according to the SmPCs of lidocaine/prilocaine and the capsaicin patch.
- studies using cutaneous capsaicin patch 8% have demonstrated that this regimen is suitable to cause epidermal denervation in healthy subjects (10).

5.6 Dosages, dosage modifications and method of administration

- the route and dosage of lidocaine/prilocaine and the capsaicin patch is being used according to the SmPCs of lidocaine/prilocaine and the capsaicin patch.
- a small patch of 8% capsaicin will be applied to the middle finger for 60 minutes.

5.7 Preparation and labelling of Non Investigational Medicinal Product

- lidocaine/prilocaine cream will be present at the outpatient clinic of the Dept. of Neurology and supplied from regular pharmacy stock
- capsaicin 8% patches will be delivered to Erasmus MC by the manufacturer in their original packaging, cut to size on- site and used within 2 hours of opening the package.

5.8 Drug accountability

All treatments for the study will be dispensed from the Department of Clinical Pharmacy of Erasmus MC. Drug accountability will be done in accordance with the pertaining SOPs of the pharmacy. Unused lidocaine/prilocaine crème will be returned to the pharmacy at the end of the clinical phase. Waste capsaicin patches will be destroyed along with other medical waste at Erasmus MC.

METHODS

5.9 Study parameters/endpoints

5.9.1 Main study parameter/endpoint

- magnitude and time course of the flavoprotein response
- linearity of the electrical stimulation with the flavoprotein response
- block of the flavoprotein response by lidocaine / prilocaine cream and 8% capsaicin patches

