Figure 2: high density of nociceptor endings in the epidermis, demonstrated by immunohistochemical staining with PGP9.5. The endings have a somewhat "variceus" aspect. In these thickenings there is a high concentration of mitochondria (see figure 3).

Figure 3: electron microscopic recording of an axon terminal (A) and Schwann cell (SC) of a nociceptor termination. The arrow shows 11 mitochondria in this ending.

Figure 4: sharp decrease in the number of epidermal nociceptor endings in an animal model for neuropathy. sham = control animal, CCI = animal with chronic constriction injury (model

for neuropathy), u.dermis is upper dermis. The arrowheads show PGP9.5 labeled epidermal nociceptor endings, which are completely absent in the epidermis in the animal with neuropathy.

OBJECTIVES

Primary Objective:

To study whether painful neuropathy can be measured with flavoprotein imaging, first of all a pilot study is needed, with which we want to investigate whether a reproducible and validated flavoprotein signal can be obtained at the second fingertip of healthy subjects.

STUDY DESIGN

- studying whether there is a time relationship between administering an electrical stimulus by means of finger electrodes and an optical (flavoprotein) signal on the fingertip of test subjects
- studying whether there is a linear relationship between the strength of the applied electrical signal and the size of the optical (flavoprotein) signal
- studying whether the signal is specific to the flavoprotein wavelength, by changing the filter settings of the camera
- studying whether the optical (flavoprotein) signal can be blocked by administering lidocaine / prilocaine cream on the fingertip
- studying whether the optical (flavoprotein) signal can be blocked by administering a capsaicin 8% patch on the fingertip.

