5.11 Study procedures

- 1) Each subject will undergo a series of electrical stimuli (5Hz, for 10 seconds) with AFI measurement. Each stimulus strength (0.5, 0.6, 0.7, 0.8, 0.9 and 1.0 mA) will be administered twice. The stimulus is interrupted when the pain intensity exceeds 7. Thereafter, a (non-painful) 2000Hz, 1.0mA stimulus will be administered as a (negative) control for 10 seconds. The stimuli are administered by a Neurometer, a validated before (11). The middle finger is illuminated with a white light source, from which blue light with a wavelength of 480nm is filtered. This light excites oxidized flavoproteins. The signal is picked up by a digital camera that is connected to an upright microsoop. The stimulation and measurements take 15 minutes.

- 2) At the end of the above measurements, the middle finger tip is smeared with lidocaine / prilocaine cream. An hour later the test person returns for the same measurements described above (15 minutes).
- 3) At the end of the measurements described under 2) an 8% capsaicin patch is applied to the middle finger tip. After an hour the researcher comes along and the plaster is removed. A week later the test person returns to undergo the measurements as described under 1) again (15 minutes).

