5.13 Replacement of individual subjects after withdrawal

If test subjects lose weight, other test subjects will be approached, so that there are at least 10 participants in the (pilot) study

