7. STATISTICAL ANALYSIS

7.1 Primary study parameter(s)

-corelation coefficients between stimulus strength and AFI signal amplitude will be calculated. The statistical significance of the correlation will be calculated using linear regression analysis.

-repeated-measures ANOVAs will be performed between baseline recordings and recordings 1 hour after application of lidocaine/prilocaine cream and between baseline recordings and recordings 1 week after application of a capsaicin patch. Finally, a paired t-test will be used to compare 1.0mA, 5Hz and 1.0mA, 2000Hz electrical stimulation.

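### The main endpoint is block of the flavoprotein response, but its only named analysis is an undirected test of no change, which cannot tell a partial fall from a block

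*Protocol*

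**What the plan says.** The Study Design section puts the question for the cream as "studying whether the optical (flavoprotein) signal can be blocked by administering lidocaine / prilocaine cream on the fingertip" and asks the same of the capsaicin patch. Section 5.9.1 carries this into the main endpoints as "block of the flavoprotein response by lidocaine / prilocaine cream and 8% capsaicin patches". Section 3 gives the role of the two products: their use "is not the aim of the study, but serves as a negative control".

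For this endpoint 7.1 states that "repeated-measures ANOVAs will be performed between baseline recordings and recordings 1 hour after application of lidocaine/prilocaine cream", and likewise "between baseline recordings and recordings 1 week after application of a capsaicin patch". It names no other analysis for block, and no size of reduction, remaining level or reference response.

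On the data, 5.11 says "Each stimulus strength (0.5, 0.6, 0.7, 0.8, 0.9 and 1.0 mA) will be administered twice" at 5 Hz, followed by a non-painful 2000 Hz, 1.0 mA control stimulus. The later sessions repeat the same measurements, so the 2000 Hz control is recorded in all three. Section 7.1 uses it only in a paired t-test against 5 Hz stimulation at 1.0 mA. Section 5.13 replaces drop-outs "so that there are at least 10 participants in the (pilot) study". Section 2.4 says that no data exist from which to calculate a sample size.

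**The concern.** Block means that the response is abolished, or nearly so. The named ANOVA asks whether the mean response differs from baseline at all. These are different questions, and either outcome of the test can mislead:

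- **Significant.** The response changed. Most of it may still be there, and because the test has no direction, a rise would also be significant.
- **Not significant.** The interval may be so wide that a large fall, even a complete one, is not excluded.

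The Introduction's rationale is that the signal arises from nociceptor endings in the epidermis. The two products are negative controls for that claim. If a large part of the signal survives them, much of it may come from something else, so the size of the remainder is the informative quantity.

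The cream session raises a further question. Section 5.4 lists "Transient local reactions at the application site such as paleness, erythema (redness) and oedema" among the common effects of the cream, and the optical recording is made on that same skin an hour after application. If such a reaction altered the recorded light, the ANOVA could not separate that from an effect on the nerve endings.

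**Working it through.** The protocol gives no effect size, SD or power, so there is no planned figure to reproduce.

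**Inputs**
- n = 10, each subject as own control (5.13).
- Two sessions per contrast: baseline against cream, baseline against patch (7.1).
- Alpha: not stated for these tests; assumed two-sided 0.05, with 0.10 and 0.025 as a range.
- SD of the within-subject change, as a percentage of the mean baseline response: unknown (2.4); assumed 20-50%, with 100% as a wide case.

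**Step 1: what the ANOVA tests.** With two sessions, the session effect has 1 and 9 degrees of freedom and equals the square of the paired t on subject means. A simulated data set of 10 subjects, 2 sessions and 6 strengths confirmed this: F = t² = 6.627, p = 0.030 by both routes.

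**Step 2: smallest significant mean fall.**

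t(0.975; 9) / √10 × SD = 2.262 / 3.162 × SD = 0.715 SD

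At alpha 0.10 the multiplier is 0.580, and at 0.025 it is 0.849.

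| SD of change (% of baseline) | Smallest significant fall | Response remaining |
|---|---|---|
| 20% | 14.3% | 85.7% |
| 30% | 21.5% | 78.5% |
| 50% | 35.8% | 64.2% |
| 70% | 50.1% | 49.9% |
| 100% | 71.5% | 28.5% |

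More than half the response can remain at a significant result whenever the SD is below 0.50 / 0.715 = about 70% of baseline. Changing alpha moves the 20-50% row range to 11.6-29.0% (0.580 × 20%, 0.580 × 50%) or 17.0-42.5% (0.849 × 20%, 0.849 × 50%).

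**Step 3: what a non-significant result can hide.** From the noncentral t with 9 df, 80% power needs a true fall of 0.996 SD. A true 30% fall has 80% power at an SD of 30%, 40% at 50% and 14% at 100%. At an SD of 100%, even a complete block has only 80% power, so about one such study in five would miss it.

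**Step 4: what an interval would show.** Treating the baseline mean as fixed, the 95% half-width for the remaining percentage is the same 0.715 SD. If the observed remainder were zero, the upper limit would be about 14% at an SD of 20%, 36% at 50% and 72% at 100%. The interval therefore shows how far block is supported, which the p-value does not.

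**Step 5: subtracting the 2000 Hz control.** Section 5.11 gives it at 1.0 mA only and apparently once per session. Assume equal, independent recording error. At 1.0 mA, a mean of two 5 Hz recordings has error variance 1/2; subtracting one control recording gives 1/2 + 1 = 3/2, three times as much. For the mean of all 12 recordings of the 5 Hz series it goes from 1/12 to 13/12, a 13-fold rise, with no matched control at 0.5-0.9 mA.

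**The case against.** **The plan never says that significance means block.** True. A reader might infer that it does, because nothing else is attached to the endpoint, but no sentence makes a significant ANOVA the criterion for block or a non-significant one the criterion for its absence. A statistical analysis plan, which is not shown, could add estimates and intervals. What stands is a mismatch between two things the protocol does state: the endpoint it words and the test it names.

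**Ten subjects make small falls harder to detect, not easier.** Correct. A reader might conclude that a modest fall will be significant here. That depends on an SD which 2.4 leaves unknown, and at 100% of baseline only a large fall would be.

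**The skin reactions should not be charged to both products.** This also stands. Section 5.4 gives about 180 minutes for the patch's burning and erythema and up to two days for hypersensitivity, while the patch recording comes a week later. The question concerns mainly the cream session, and no section says that these reactions alter the evoked signal.

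**Block is not the only evidence of specificity.** The study also examines timing, linearity, filter settings and 5 Hz against 2000 Hz, and response magnitude is itself a main endpoint. This lessens the consequence but does not give the block endpoint a fitting analysis.

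**Subtracting the 2000 Hz response is a poor main analysis.** This stands on the variances in step 5. In addition, a ratio of subtracted responses is unstable if the baseline difference is small, and non-painful does not mean nerve-silent.

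**No threshold for block could be justified in a first-use pilot.** Agreed. An interval needs none.

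**Conclusion.** The point holds as a mismatch between endpoint and analysis. Block is a main endpoint, and its only named test is undirected and against no change. A significant result shows a change, not a block. A non-significant one with 10 subjects does not show that block was absent.

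The size is conditional. At two-sided 0.05 and an assumed SD of change of 20-50% of baseline, a mean fall of 14-36% would be significant with 64-86% of the response remaining. At 100%, a fall of about 72% or more would be needed. The protocol supports no single value in that range. Nor does it support saying that the plan equates significance with block, or that skin reactions explain a change. The defect is worth correcting because a better summary is available from data the study already collects.

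**What to change.** In 7.1:

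1. For each product, estimate the percentage of the baseline 5 Hz response that remains, with a 95% CI, without subtracting the 2000 Hz response. A Fieller interval for the ratio of session means would serve, provided the baseline response is clearly above zero; a log ratio would fail when the remainder is near zero.
2. Describe a significant fall alone as reduced, not blocked.
3. Base any statement about block on the upper confidence limit of the remaining response.
4. State that a non-significant result will not be read as no block.
5. As a sensitivity analysis at 1.0 mA only, compare the 5 Hz minus 2000 Hz difference between sessions on the absolute scale, mainly to check for session-level optical changes after the cream. This removes additive changes, not proportional ones.

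The cost is a little more analysis and no new recordings. A claim of block becomes harder to make. The interval and the observed SD of change would also serve the purpose 2.4 gives the pilot, sizing a follow-up study.

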5.9.2 Secondary study parameters/endpoints (if applicable)

n.a.

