5.9.3 Other study parameters (if applicable)

n.a.

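### Block of the AFI signal is a main endpoint, but nothing recorded shows whether the cream or the patch reduced nociception, so an unchanged signal would be ambiguous

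*Protocol*

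**What the plan says.** Section 3 of the protocol (Treatment of subjects) says that the intervention with the cream and the patch "is not the aim of the study, but serves as a negative control". Section 5.9.1 lists three main parameters, all of them AFI measures; the third is "block of the flavoprotein response by lidocaine / prilocaine cream and 8% capsaicin patches". Sections 5.9.2 (secondary) and 5.9.3 (other) are both marked not applicable.

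The controls are timed in 5.11. After the cream, "An hour later the test person returns for the same measurements described above (15 minutes"). After the patch, "A week later the test person returns to undergo the measurements as described under 1) again". The series to be repeated is the one in step 1: six currents from 0.5 to 1.0 mA at 5 Hz, each given twice, then one 2000 Hz stimulus. Pain enters that step in one sentence: "The stimulus is interrupted when the pain intensity exceeds 7". The scale is not named.

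For the patch, 5.5 relies on outside evidence: "studies using cutaneous capsaicin patch 8% have demonstrated that this regimen is suitable to cause epidermal denervation in healthy subjects". For the cream, 5.5 refers to use according to the product information, and the Summary expects about 3 hours of numbness. Section 7.1 compares baseline AFI recordings with those at 1 hour and at 1 week and uses no sensory variable.

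**The concern.** A negative control is informative only if it did what it was meant to do. Here that means the nociceptor endings at the imaged fingertip were out of action, or much reduced, when AFI was recorded. The plan assumes this and keeps no reading that could show it.

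The Primary Objective asks for a validated signal, and block is the most direct test of whether the signal comes from nerve endings. Suppose AFI is unchanged after cream or patch. Either the signal is not neural, which counts against the method, or the endings were still working, which says nothing about the method. The two call for opposite decisions about a follow-up study.

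The protocol itself allows for incomplete block. Section 10.2 foresees, as a minimal risk, moderately severe burning in the fingertip from the patch even though the cream was applied an hour before.

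A statistical analysis plan could not repair this later, because it cannot analyse a reading that was not kept.

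**Working it through.** **1. What is collected and used.**

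| Place | Content | Sensory measure? |
|---|---|---|
| 5.9.1 | AFI magnitude and time course; linearity; block | No |
| 5.9.2, 5.9.3 | Not applicable | No |
| 5.11 | Pain intensity above 7 stops the stimulus | Asked for, not listed as data |
| 7.1 | Correlation and regression, repeated-measures ANOVA, paired t-test, on AFI | No |

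The stop rule also leaves little trace. If a subject stays at or below 7 at baseline, the absence of an interruption later does not show whether pain was lost.

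**2. The two readings of a null result.** The protocol states no effect size, SD, alpha or power for block, so there is no figure to reproduce. Assumptions for illustration:
- n = 10 (2.2) and a two-sided 5% test.
- One baseline-versus-block contrast, treated as a paired t-test. With two sessions the repeated-measures F equals t squared.
- Full block lowers AFI by d = 1.0 or 1.5 SD of the paired difference.
- m of the 10 subjects are unblocked and show no change.

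The mean effect is then (10 − m)/10 of full block. Power by simulation (400,000 runs per cell):

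| m unblocked | Mean effect | Power, d = 1.0 | Non-significant | Power, d = 1.5 | Non-significant |
|---|---|---|---|---|---|
| 0 | 100% | 80% | 20% | 99% | 1% |
| 1 | 90% | 68% | 32% | 94% | 6% |
| 2 | 80% | 55% | 45% | 85% | 15% |
| 3 | 70% | 42% | 58% | 70% | 30% |
| 5 | 50% | 22% | 78% | 35% | 65% |
| 10 | 0% | 5% | 95% | 5% | 95% |

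The last row is the key one. If the control fails in everyone, a neural signal gives a non-significant result 95% of the time. A signal that is not neural gives the same 95%. AFI alone cannot separate the two, and a larger n would not help.

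**3. Effect on sizing a follow-up, if it were sized on this contrast.** With unblocked fraction f, the observed standardised effect is (1 − f)d / √(1 + f(1 − f)d²). At f = 0.3:
- d = 1.0: 0.70 / √1.21 = 0.636. By the noncentral t, n for 80% power rises from 10 to 22.
- d = 1.5: 1.05 / √1.4725 = 0.865. The n rises from 6 to 13.

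**4. What the missing reading would add.** Each session has 6 × 2 + 1 = 13 stimuli, so three sessions give 39 ratings per subject and 390 in all. Pain and AFI would then be paired at the same current, in the same subject, before and after each agent.

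**The case against.** Five points can be made for the plan.

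- **Pain is already elicited in every session.** Sessions 2 and 3 repeat the full stimulus series, stop rule included, and case report forms that are not public may hold the ratings. This stands. A reader might infer that nothing sensory is asked after cream or patch, and the text does not support that. The gap is that the rating is not a listed parameter and has no role in the analysis.
- **The patch regimen rests on a cited study.** Its title names long-term effects on epidermal nerve fibre density and sensory function in healthy volunteers. Relying on it is defensible in a pilot. A reader might infer that denervation is likely to be absent at the fingertip after one week, but nothing in the protocol says so. The study still does not verify block in these fingers, and it does not cover the cream.
- **Block is one of several lines of evidence.** Two agents are used, and there are also the time relation, linearity, the wavelength check and the 2000 Hz control. This limits the damage, but none of the others shows whether an agent worked.
- **With n = 10, a check on block would not settle a null result.** Correct. At d = 1.0, even 10 fully blocked subjects give a non-significant result 20% of the time. The planned reading must allow for this.
- **Sensory testing is subjective and laborious, as the Introduction says.** That argues against adding pinprick or heat tests, which also use a different stimulus from the electrical one that evokes the AFI signal. It is no argument against keeping a rating that is already asked for.

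**Conclusion.** The point holds as a gap in what is recorded and reported. The block endpoint has no within-subject evidence that either agent reduced nociception, so an unreduced AFI signal cannot be assigned to a non-neural source rather than to a failed control.

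The reach is limited. A reader might conclude that the whole block endpoint is uninterpretable. It is not: an observed block remains interpretable, and only a null or weak result is affected. Nor does the protocol show that the controls will fail; section 10.2 shows only that incomplete protection by the cream was foreseen.

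The 95% figure for complete failure follows from the 5% test level and does not depend on d. The loss of power from partial failure (80% to 42%, or 99% to 70%, with 3 of 10 unblocked) rests on assumed effect sizes and failure rates. The consequence for a follow-up sample size is conditional too, because 2.4 says only that the pilot's results will be used, not that the block contrast will be. This is a cheap improvement to a pilot meant to validate a signal, not a flaw that stops it.

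**What to change.** 1. In 5.11, name the pain scale. Record the pain intensity for every stimulus in all three sessions, and whether the stimulus was interrupted.
2. List these in 5.9.2.
3. In the analysis, report the change from baseline in pain at matched current beside the AFI change, for each agent and for all 10 subjects. Do not restrict the report to subjects judged to be blocked.
4. State the reading in advance. Unchanged AFI with clearly reduced pain is evidence against neural origin, limited by n = 10. Unchanged AFI with unchanged pain is inconclusive.

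The cost is slightly more recording: 13 ratings per session, with no extra visit and no new procedure, since the stop rule already requires asking. The rating has limits. It is subjective, the subject knows which agent was applied, and a stimulus that hardly hurt at baseline leaves no room for a fall. These are reasons to report it as supporting information, not as a formal criterion.
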